8.1.4. Pharmacokinetic Endpoint

- PK of voxelotor as evaluated by population PK analysis using nonlinear mixed effects modeling.

8.2. Sample Size

The sample size for the entire study, including Groups 1, 2 and 3, is estimated to be approximately 370 participants (up to a maximum of approximately 435 participants, depending on the dose[s] selected for the Group 3). Refer to the Study Schematic in [Figure 1](#) and [Section 2.1](#).

For analysis purposes, data from all participants in Groups 1 and 2 will be combined to form the basis of the primary analysis of the study.

8.2.1. Group 1

The primary efficacy measure, Hb, will be evaluated as 2 endpoints:

- as change from Week 12 to Baseline
- as a responder endpoint (change from Week 12 to Baseline >1 g/dL)

For the endpoint of change from Baseline in Hb, power calculations assume a mean treatment effect of 0.8 g/dL (voxelotor at either dose, minus placebo), the placebo change from Baseline is equal to 0, a per-group SD of 0.6 g/dL. With N = 20 participants per arm, the power exceeds 95% of detecting a treatment difference between either voxelotor dose (900 mg or 1500 mg) versus placebo. Power is calculated for the t-test and assumes that the data are normally distributed. The estimates of 0.8 g/dL and 0.6 g/dL for the treatment effect and SD, respectively, are based on data at Day 90 from Cohorts 16 and 17 from a previous study.

For the responder endpoint at Week 12, the voxelotor doses will be pooled. Assuming responder proportions of 35% and 5% for N = 40 after pooling data from the 900 and 1500 mg groups and placebo (N = 20), respectively, the power with Fisher's exact test at a two-sided alpha = 0.05 is 80%.

8.2.2. Group 2

Group 2 is designed to allow continued enrollment between Group 1 and Group 3 while the Group 1 data collection and analysis with a minimum of 12 weeks of follow up and until decision is made on voxelotor dose selection for Group 3. Group 2 sample size was estimated based on these considerations and no formal statistical assessment was performed.

Based on the results from Group 1 analysis (62 participants), and a second analysis which included 94 subjects from Group 2 (total of 156 participants) with a minimum of 24 weeks of follow up, it was decided that the combination of Group 1 and all Group 2 participants, for a total of 274 randomized subjects, would constitute the basis for the primary analysis of the study.

For the primary analysis of hemoglobin response rate comparing voxelotor 1500 mg to placebo, assuming a 10% Hb response rate in placebo, the study with approximately 90 subjects per treatment group will have >95% power to detect a targeted difference of 30%, using Fisher's exact test with a two-sided alpha of 0.0481 (Section 8.4.3).

8.2.3. Group 3

Group 3 sample size will be determined when the voxelotor dose(s) is selected. Additional considerations may also be generated on the basis of key findings in the primary analysis from Groups 1 and 2.

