8.4.3. Interim Efficacy Analysis

Two interim analyses (IA) are planned to inform voxelotor dose selection. The first IA was performed with Group 1 data (n=62), followed by the second IA with the combined Groups 1 and 2a (n=156).

The Main Analysis will be performed based on data from all randomized subjects in Group 1 and Group 2 (n=274). A Lan-DeMets alpha spending function with the O'Brien-Fleming boundary is used to determine the significance level for each IA and the Main Analysis, to maintain an overall type I error rate of 5% (two-sided), resulting in the following:

Analysis	Significance Level (two-sided)
IA #1 (n = 62)	0.000005
IA #2 (n = 156)	0.0059
Primary Analysis (n = 274)	0.0481

PASS Software (version 11) was used to calculate the alpha spending for each analysis (two-sample proportion).

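### Protocol 8.2.1 states 80% power for the Group 1 responder comparison where the named test gives 77.9%, and it does not say how its nominal 0.05 relates to the interim level in 8.4.3

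*Protocol*

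**What the plan says.** Protocol Section 8.2.1 sizes Group 1 on two Week 12 haemoglobin endpoints.

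- **Responder endpoint.** The two voxelotor doses are pooled: "Assuming responder proportions of 35% and 5% for N = 40 after pooling data from the 900 and 1500 mg groups and placebo (N = 20"). The section then says that power by Fisher's exact test "at a two-sided alpha = 0.05 is 80"%.
- **Change from baseline.** The "power calculations assume a mean treatment effect of 0.8 g/dL (voxelotor at either dose, minus placebo"), with "a per-group SD of 0.6 g/dL". "With N = 20 participants per arm, the power exceeds 95% of detecting a treatment difference" for either dose against placebo. The method is named ("Power is calculated for the t-test and assumes that the data are normally distributed"), but no alpha is given. The opening of Protocol Section 8 sets a default of two-sided 0.05 unless otherwise stated.

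Protocol Section 8.4.3 and SAP Section 6.3.3 list the Group 1 analysis (n = 62) as the first of two interim analyses that inform dose selection. A Lan-DeMets spending function with an O'Brien-Fleming boundary "is used to determine the significance level for each IA and the Main Analysis". The listed two-sided levels are 0.000005, 0.0059 and 0.0481, calculated for a two-sample proportion. Section 8.2.2 states the primary-analysis power at 0.0481 and cites 8.4.3. Section 8.2.1 makes no such reference.

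**The concern.** There are two points, both small.

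First, the 80% is stated without qualification, and the test, alpha, rates and sample sizes are all given beside it. A reader can recompute it, and the result is lower.

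Second, the protocol attaches two significance levels to the Group 1 analysis, 0.05 in 8.2.1 and 0.000005 in 8.4.3, without saying what each is for. The primary-analysis power was tied to the alpha-spending plan by a cross-reference, and the Group 1 powers were not. A reader who goes from one section to the other cannot tell whether 80% and >95% describe a nominal comparison that helps choose a dose or a test at the interim boundary.

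What is at stake is the accuracy of a planning figure and the clarity of a section. Neither the sample size nor the inference from the trial depends on it.

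**Working it through.** **1. Responder power by the named test**

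Inputs (Protocol 8.2.1): p_v = 0.35, n_v = 40; p_c = 0.05, n_c = 20; Fisher's exact test, two-sided 0.05.

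Power = sum over all (x, y) of Bin(x; 40, 0.35) × Bin(y; 20, 0.05) × 1[two-sided Fisher p ≤ 0.05], taken over all 41 × 21 outcomes.

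The sum can be set out by the number of placebo responders y. The third column is the smallest number of voxelotor responders that rejects in favour of voxelotor.

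| y | P(y) | x needed | P(reject given y) | product |
|---|---|---|---|---|
| 0 | 0.3585 | 8 | 0.9876 | 0.3540 |
| 1 | 0.3774 | 11 | 0.8785 | 0.3315 |
| 2 | 0.1887 | 15 | 0.4279 | 0.0807 |
| 3 | 0.0596 | 17 | 0.2022 | 0.0120 |
| 4 | 0.0133 | 20 | 0.0363 | 0.0005 |

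Larger y adds less than 0.0001. The total before rounding is 0.7788, so the power is **77.9%** against the stated 80%, a gap of 2.1 points.

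**2. Could another reading give 80%?**

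| Variant | Power |
|---|---|
| Fisher, 41 vs 21 (or 42 vs 20), i.e. n = 62 | 78.6% |
| Fisher, 40 vs 20, but 36% vs 5% | 80.2% |
| Fisher, doubled one-sided p | 73.6% |
| Fisher, one-sided 0.05 | 81.3% |
| Fisher, mid-p | 82.8% |
| Pearson chi-square (exact enumeration) | 81.3% |
| Normal approximation, pooled variance | 77.4% |
| Normal approximation, unpooled variance | 91.6% |
| Normal approximation, continuity-corrected | 63.1% |
| Arcsine | 84.5% |

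The documents do not give the arm split of the 62, so 41/21 and 42/20 are assumptions. None of the variants that reach 80% uses both the named test and the stated inputs.

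**3. Change in haemoglobin**

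Inputs (Protocol 8.2.1): difference 0.8 g/dL, SD 0.6 g/dL, 20 per arm, t-test with 38 degrees of freedom. Alpha is taken from the default in Section 8.

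Noncentrality = 0.8 / (0.6 × √(2/20)) = 4.216. The critical value at two-sided 0.05 is 2.024. Power = 98.4%, so the statement of >95% reproduces.

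**4. The interim level**

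O'Brien-Fleming-type spending, two-sided: 4 × [1 − Φ(z(1 − 0.05/4) / √f)].

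- f = 62/274 = 0.226 gives 0.0000049.
- f = 156/274 = 0.569 gives 0.0059.

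Both agree with the table in 8.4.3.

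**5. Power at 0.000005, if that level applied to these tests**

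- Pooled responder, Fisher, 40 vs 20: 0.11%. With no placebo responders, 23 of 40 on voxelotor would be needed.
- Change in haemoglobin, t-test, 20 vs 20: the critical value is 5.311 and the power 18.3%.

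These two figures are conditional, because no section assigns 0.000005 to either comparison.

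**The case against.** The strongest reply is that nothing turns on this. The gap is about two points, 36% instead of 35% would close it, and 35% is itself a planning assumption. Group 1 has been enrolled, unblinded and analysed. The SAP, which supersedes the protocol where applicable, gives only the confirmatory power, correctly tied to 0.0481. All of that stands and sets the size of the point. It does not make 80% the power of the named test on the stated inputs.

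A reader might go further and infer that the Group 1 analysis really has 0.1% and 18% power, so that 8.2.1 misleads about what the analysis could show. The documents do not support this:

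- The 0.000005 was calculated for a two-sample proportion. The formal testing sequence starts with haemoglobin response at Week 24, 1500 mg against placebo. The powers in 8.2.1 are for a pooled-dose Week 12 responder test and a Week 12 t-test on change. The 18% is the weaker of the two figures, since it puts a boundary derived for proportions on a continuous endpoint.
- Alpha 0.05 is stated only for the responder power. For the t-test it is inferred from the default.
- Protocol 2.1.2, 6 and 8.4.3 and the SAP introduction all say that the analysis informs dose selection. Very low power at 23% information is what an O'Brien-Fleming-type boundary gives, and is not a design failure.

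**Conclusion.** The point holds as a small numerical correction with a clarification. On the inputs and test in Protocol 8.2.1, the responder power is 77.9%, not 80% (78.6% if the 62 are split 41/21). The >95% for change in haemoglobin is correct, at 98.4%, taking the default two-sided 0.05. Section 8.2.1 should say that its powers are nominal, because 8.4.3 lists a different level for the same analysis and the two sections are not linked.

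The primary analysis is unaffected: 10% against 40% with 90 per arm at 0.0481 gives 99.7% by Fisher's exact test, in line with the stated >95%. The 77.9% rests only on figures printed in 8.2.1 and on the usual two-sided Fisher p-value (summing outcomes no more probable than the one observed). The documents do not support reading 0.1% and 18% as the actual powers of the Group 1 analysis.

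**What to change.** In Protocol 8.2.1:

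1. Restate the responder power as about 78%.
2. Add one sentence: the Group 1 powers are at a nominal two-sided 0.05 to support dose selection, and are not powers at the first interim significance level (0.000005) in Section 8.4.3.

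Figures at the interim level need not be added. If they are quoted, mark them as conditional on that level applying to the test in question (about 0.1% for the responder comparison, 18% for change in haemoglobin). A new statement that no efficacy claim may be made at the first interim analysis is not needed: it would add a rule that sits awkwardly with 8.4.3, which assigns that analysis a level.

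The cost is one changed number, one sentence and a slightly less favourable stated power. No analysis, sample size or trial conduct changes.

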8.3. Populations for Analysis

The following populations will be considered in the analysis of data. Assignment or exclusion of participants from the analysis populations will be performed prior to study unblinding.

- **Safety Population**: All participants who receive any amount of study medication will be included in the Safety Population. Participants will be analyzed based on medication received. This is the primary population for demography and safety data.
- **Intent to Treat (ITT) Population**: Efficacy analyses will be performed on the ITT population which includes all randomized participants.
- **Modified Intent-to-Treat (mITT) Population**: mITT population includes all randomized patients who received at least one dose of study treatment.
- **PK Population**: The PK Population will consist of all participants who receive active study drug and have at least one measured concentration at a scheduled PK time point after the start of dosing. If any participants are found to be noncompliant with respect to dosing or have incomplete data, protocol violations, or clinical events that affect PK, a decision will be made on a case-by-case basis as to their inclusion in the analysis. Participants in this population will be used for all PK summaries.

8.4. Analysis

The primary analyses (based on data from all Group 1 and 2 participants) will adjust for the randomization stratification factors. For the Group 1 population, due to the smaller sample size, adjustment will be made only for a single stratification factor. The factor that will be selected will be the one for which the imbalance between the largest and smallest strata level is the smallest. If both voxelotor dose groups are selected in the primary analysis, the comparisons will be of each voxelotor dose versus placebo, and will be adjusted for multiplicity.

8.4.1. Efficacy Analysis

8.4.1.1. Primary Endpoint

Hb response rate will be analyzed using an exact Cochran-Mantel-Haenszel (CMH) general association test. Each voxelotor dose group (900 mg and 1500 mg) will be compared to placebo while stratifying for the randomization stratification factors as appropriate. The primary analysis of Hb response rate will be to compare voxelotor 1500 mg vs placebo. The test hypotheses are as follows:

$$H_0: p_v = p_c \quad \text{vs} \quad H_a: p_v \neq p_c$$

where p_v is the Hb response rate in voxelotor 1500 mg group and p_c is the Hb response rate in the placebo group.

Change from baseline in Hb over time will be analyzed using a mixed effect for repeated measures (MMRM) model. The fixed effect terms include treatment, study visit, treatment by visit interaction, and randomization stratification factors as appropriate. Within-subject variability will be modeled using an unstructured covariance matrix.

The adjusted mean (lsmean) change from baseline in Hb at each visit, estimated from the MMRM model, with the estimated standard error and 95% confidence interval (CI), will be presented. The difference in the adjusted means between treatment groups and the associated 95% CI of the difference will be provided.

Hb worsening will be summarized using a shift table for each treatment group. Incidences of post-baseline Hb < 5.5 g/dL will be summarized by treatment group, as well as incidences of Hb change from baseline < -2 g/dL.

Proportion of subjects with Hb of ≥ 10 g/dL at Week 24 will be explored.

All analyses specified above will be based on data with imputation for RBC transfusion, and VOC and VOC hospitalization as applicable. The analysis of Hb response rate will also be repeated using observed data without imputation to assess the robustness of the data.

8.4.1.2. Secondary Endpoints

8.4.1.2.1. Change from Baseline to Week 24 in Hemolysis Related Measures

Percent change from baseline over time in unconjugated bilirubin, absolute reticulocyte, reticulocytes %, and LDH will be analyzed with a similar MMRM model as for change from baseline to Week 24 in Hb.

In addition, the absolute and percent changes from Baseline to Week 24 in each hemolysis measure, including absolute reticulocyte, reticulocytes %, and unconjugated bilirubin will be presented descriptively via tabulation of descriptive statistics by treatment group.

8.4.1.2.2. VOC up to Week 72

The number of VOC events will be modeled using a negative binomial model with the independent variable of treatment group and adjusted for the stratification factors used for randomization. Additional risk factors, including number of VOC occurrences during the 12 months prior to randomization, will also be explored.

The mean cumulative function of VOC events will be presented using recurrent events analysis methods.

Annualized incidence rate will be summarized for each treatment group.

For Group 1 analysis, the proportion of days with SCD exacerbation will be analyzed by a fixed effects linear model. Change from Baseline in the TSS will be analyzed with an MMRM. The rate of VOC will be analyzed by the CMH row means scores test. Given the size and duration of the study at the time of the Group 1 Analysis, the recurrent event rate is expected to be low. However, negative binomial regression analyses will be performed if justified by the distribution of event rates.

8.4.1.3. Exploratory Endpoints

Kaplan Meier methods will be used to summarize time-to-event endpoints, including time to first VOC, time to first ACS and time to first RBC transfusion. Event rates will be estimated at landmark time points, eg, Week 12, Week 24, Week 48, as appropriate.

Rate of opioid use, and rate and reasons for RBC transfusion will be summarized descriptively by treatment group.

EQ-5D-L health questionnaire, Clinical Global Impression (CGI), will be summarized descriptively by treatment group.

8.4.2. Handling of Missing Data and Data Post-Transfusion

Full details of how missing data will be handled will be described in the SAP. The general rule is assigning the most recent score for missing data due to VOC, hospitalization for VOC, and the most recent score for RBC transfusions regardless of whether or not data are missing. The general guidelines regarding how missing data will be handled are described below. It is anticipated the participant dropout rate will be less than 10%.

8.4.2.1. Hemoglobin Responder

- Missing endpoint visit data due to dropout, VOC, or VOC hospitalization: participant will be treated as a non-responder.
- RBC transfusions: For participants who receive a transfusion due to anemia on or 8 weeks (primary analysis) or 12 weeks (sensitivity analysis) before the endpoint visit, the participant will be treated as a non-responder.

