6.2.1.2. Unblinding for Laboratory Test Assessment

Local laboratory tests including hematology laboratory tests may be used as needed per standard of care to manage AEs (such as hospitalization for VOC), and in these circumstances, the laboratory data may need to be unblinded.

Because knowledge of certain laboratory assessments (Hb, hematocrit [Hct], RBC count, total and unconjugated bilirubin, and absolute and % reticulocyte count) may suggest the treatment assignment, these measurements will be redacted to the Investigator and monitored on a regular basis by the DSMB. Results of redacted laboratory tests will be communicated to the Investigator if a participant's absolute reticulocyte count declines to $<80 \times 10^9/L$ or Hb declines to <5.0 g/dL or if the Hb declines ≥ 3 g/dL from screening. (but this does not require breaking of the treatment assignment blind). This is to ensure participant safety by allowing the Investigator to monitor for potential bone marrow suppression, as described in hydroxyurea (HU) monitoring guidelines (NHLBI 2014) (National Heart, Lung, and Blood Institute; NHLBI, 2014). All other laboratory assessments (not redacted) will be available to the Investigator. Anonymized laboratory results will be available to the Sponsor.

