Hemoglobin (Hb) response is based on the difference between the average value of Hb levels at Week 20 (Hb20) and Week 24 (Hb24) and baseline Hb level (HbB). A subject is considered to be a Hb responder if $[\text{mean}(\text{Hb20}, \text{Hb24}) - \text{HbB}] > 1 \text{ g/dL}$. If Hb20 or Hb24 is missing, then the calculation will use the non-missing Hb level. Regardless of calculated difference, subjects will be classified as a non-responder if any of the non-responder criteria in [Section 6.3.5.1](#) are met.

Hemoglobin Worsening at Week 24

- Severe anemic episode - worst Hb between weeks 12 and 24 inclusive is $< 5.5 \text{ g/dL}$
- Acute anemic episode - worst Hb between weeks 12 and 24 inclusive, is $\geq 5.5 \text{ g/dL}$ and $< 7 \text{ g/dL}$

Rate of Opioid Use During Treatment Period

The rate of opioid use is calculated as the number of days opioids were taken for SCD symptom management (as recorded in the eDiary) divided by the number of days with non-missing eDiary data from date of randomization to date of last dose.

Total Symptom Score (TSS)

For each subject, the TSS will be computed as follows: The Baseline TSS is the average of the scores during the 28 to 35-day Screening period. Similarly, post randomization when there is at least 75% compliance during a 4-week period, the TSS is the average score for each 4-week period. The 4-week periods are Weeks 1-4 (Study Day 1-28), Weeks 5-8 (Study Day 29-56), and Weeks 9-12 (Study Day 57-84) and follows similarly for subjects whose involvement exceeds 12 weeks up to Week 24. If there is a delay in initiating study treatment, all TSS data prior to administering treatment will be included with the Screening period data. All TSS data post dose through Study Day 28 will constitute Weeks 1-4. If missing data in a 4-week period is due to lack of compliance or subject dropout, the TSS will be set to missing for the 4-week period. Missing data due to VOC, VOC hospitalization or RBC transfusion will be imputed as described

in Section 6.3.5. Compliance of at least 60% during each 4-week period will also be examined in a sensitivity analysis for TSS.

TSS₁₀₀ is TSS rescaled from a 27-point scale to 100-point scale. Algebraically, this is accomplished as follows:

$$TSS_{100} = TSS \times \frac{100}{27}.$$

Clinical Global Impression of Change

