6.3.5.1. Hemoglobin Responder

- If Hb assessment is missed at both Week 20 and Week 24 due to dropout, VOC, or VOC hospitalization: Subject will be treated as a non-responder. If Hb at one of the two time points is non-missing, Hb response assessment will be based on the non-missing Hb value.
- Initiation of HU post randomization and prior to Week 24: Subject will be treated as a non-responder.

[figure not shown]
- RBC transfusions: A participant who receives a transfusion due to anemia within 8 weeks (12 weeks for sensitivity analysis) of the Week 24 Hb assessment will be deemed a non-responder. For subjects receiving transfusion due to reasons other than anemia within 8 weeks (12 weeks for sensitivity analysis) of the Week 24 Hb assessment, Week 24 Hb will be imputed with the last Hb assessment prior to the transfusion.

Example: In Figure 1, an RBC transfusion due to anemia occurred at Day 114. If the Week 24 Hb assessment occurs before Day 170 then the participant will be deemed a non-responder; otherwise the Week 24 Hb measure will then be compared to Baseline to determine whether the participant meets the definition of responder (i.e. $8.1 - 7.95 = 0.15$, which is classified as a non-responder). If the RBC transfusion is not due to anemia, then the Hb assessment prior to Day 114 (i.e., the Week 12 assessment, which is 7.0 g/dL) will be used for imputation of Hb for assessments occurring from Study Day 114 to Study Day 170 (8-week imputation) or to Study Day 198 (12-week imputation). The Week 24 Hb measure will then be compared to Baseline to determine whether the participant meets the definition of responder.

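### The primary Hb response rule turns on an undefined recorded reason for transfusion, and no planned analysis tests how far the estimated effect depends on it

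*Protocol*

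**What the plan says.** Response means that the average of the Week 20 and Week 24 Hb exceeds baseline by more than 1 g/dL. SAP Section 4 adds an override: "subjects will be classified as a non-responder if any of the non-responder criteria in" SAP 6.3.5.1 are met.

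Transfusions are split by reason:

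- **Attributed to anemia.** Protocol 8.4.2.1: "For participants who receive a transfusion due to anemia on or 8 weeks (primary analysis", or 12 weeks in the sensitivity analysis, the participant is a non-responder. SAP 6.3.5.1 agrees: "A participant who receives a transfusion due to anemia within 8 weeks (12 weeks for sensitivity analysis) of the Week 24 Hb assessment will be" scored as a non-responder.
- **Any other reason.** SAP 6.3.5.1: "For subjects receiving transfusion due to reasons other than anemia within 8 weeks", "Week 24 Hb will be imputed with the last Hb assessment prior to the transfusion". The result is then compared with baseline and may be a response.

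Neighbouring rules do not use the reason for transfusion. The general rule in Protocol 8.4.2 takes "the most recent score for RBC transfusions regardless of whether or not data are missing". The rules for Hb change (Protocol 8.4.2.2) and for hemolysis measures (SAP 6.3.5.2) also carry the earlier value forward whatever the reason. Within the responder rule, other events are failures outright: starting hydroxyurea before Week 24, and the case "If Hb assessment is missed at both Week 20 and Week 24 due to dropout, VOC, or VOC hospitalization".

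Two checks on the responder analysis are planned: the 12-week window, and a repeat on observed data without imputation (Protocol 8.4.1.1, SAP 8.2.1.2). Reasons for transfusion are summarized descriptively by arm (SAP 8.2.3.1).

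**The concern.** The same transfusion on the same day can make a participant a certain failure or a possible responder, depending on one recorded reason. The published text does not define when a transfusion is due to anemia, say who decides, or provide for blinded adjudication.

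Hb is the endpoint, and it may also inform that reason. Central Hb is redacted to the investigator, but Protocol 6.2.1.2 says "Local laboratory tests including hematology laboratory tests may be used as needed per standard of care to manage AEs (such as hospitalization for VOC", so a local value may be known when the reason is recorded.

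At stake is the size of the estimated difference in response rates, for the primary test (1500 mg) and for hypothesis 5 (900 mg). The planned checks do not isolate this dependence. The 12-week analysis widens the window but keeps the split. The observed-data repeat drops the carry-forward, but it then uses Hb that the transfusion itself may have raised.

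**Working it through.** **1. The plan's own figure.** SAP 6.1 gives 10% response on placebo, a 30-point difference (so 40% on 1500 mg), about 90 per arm, Fisher's exact test and two-sided alpha 0.0481. Exact enumeration gives power 99.7%, consistent with the stated >95%.

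**2. What the carried value can replace.** In the SAP example the transfusion is on Day 114, and the imputation runs to Day 114 + 56 = 170 (12 weeks: 114 + 84 = 198). The Week 20 and Week 24 target days are 140 and 168 (SAP Table 1). Both fall inside the period, so a Week 12 value can stand for both.

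**3. Size.** The documents give no transfusion rate, no split of reasons and no response status before transfusion, so these are assumptions:

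- x = share of each arm transfused in the window (5% to 15%)
- m1, m0 = share of those transfusions attributed to anemia on voxelotor and placebo
- p1 = 0.40, p0 = 0.10 = response among the untransfused and on the carried value. These are the design rates from SAP 6.1, borrowed for this purpose.

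The difference in response rates under three rules:

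- every transfusion a failure: (1 − x)(p1 − p0)
- the plan: (1 − x)(p1 − p0) + x[(1 − m1)p1 − (1 − m0)p0]
- carry-forward for all: p1 − p0 = 30 points

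| x | m0 / m1 | All fail | Plan minus all fail | Plan | Plan minus carry-forward for all |
|---|---|---|---|---|---|
| 5% | 0.8 / 0.5 | 28.5 | 0.05(0.20 − 0.02) = 0.9 | 29.4 | −0.6 |
| 10% | 0.5 / 0.5 | 27.0 | 0.10(0.20 − 0.05) = 1.5 | 28.5 | −1.5 |
| 10% | 0.7 / 0.3 | 27.0 | 0.10(0.28 − 0.03) = 2.5 | 29.5 | −0.5 |
| 15% | 0.7 / 0.3 | 25.5 | 0.15(0.28 − 0.03) = 3.75 | 29.25 | −0.75 |

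Over a wider set of scenarios, including unequal transfusion shares, the excess over all-fail runs from 0.15 to 6.0 points. The gap to carry-forward for all runs from −3.75 to +1.5 points. That gap is x(m0·p0 − m1·p1), which is positive only if m0 > 4·m1 at these rates.

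**4. A label that follows Hb.** A simulation used one labelling rule in both arms, driven by pre-transfusion Hb (assumed baseline 8.5 g/dL, SD 1.0; change SD 0.85; effect 0.8 against 0; 10% transfused). The plan's difference is 27.2 points with a label unrelated to Hb and 28.6 with a strongly dependent one. All-fail gives 25.8 to 25.9, and carry-forward for all 28.7 to 28.8. Over 5% to 20% transfused, the dependence adds about 0.3 to 2.7 points. Part of this arises because fewer transfusions are labelled anemia in both arms: at 10% transfused the share falls from 50% to 18% on voxelotor and 36% on placebo.

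**5. No effect on Hb.** If voxelotor does not change Hb, then p1 = p0, and a label driven by Hb has m1 = m0, so the plan's difference is 0. If labels differed by arm for some other reason (10% anemia on voxelotor, 90% on placebo) with 10% response in both arms, Fisher rejection is 2.8%, 2.9% and 3.2% at 5%, 10% and 15% transfused, below 4.81%. It reaches 5.2% only at 30% transfused.

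**6. Power if every transfusion fails.** At x = 5% (38% against 9.5%) it is 99.5%; at x = 15% (34% against 8.5%) it is 98.8%.

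**The case against.** A reader might infer that the rule biases the primary endpoint toward voxelotor. The documents do not support that as a general statement.

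- **The excess depends on the comparator.** Counting every transfusion as failure is a different estimand, not a neutral truth. All four tabulated scenarios give 28.5 to 29.5 points, below the assumed 30. Both rules attenuate the effect, and all-fail attenuates it more. This stands.
- **Part of the excess is the treatment effect itself.** The carried value is more often a response on voxelotor because voxelotor is assumed to raise Hb. With equal labels, the 1.5 points is real effect that is not set to zero. This stands.
- **Differential labelling is conjecture.** Treatment is double-blind, central Hb is redacted, and a transfusion given because Hb is low is reasonably a failure on an Hb endpoint. It stands that no passage shows labels differing by arm. It does not remove the dependence on an undefined label that local Hb may inform.
- **Checks exist.** Descriptive tables of reasons could reveal an imbalance, and the observed-data repeat removes the carry-forward. Neither shows the response difference with the label taken out.
- **The Week 20 to 24 gap is partial.** A transfusion after Week 20 leaves a genuine Week 20 Hb, which covers about half the window (Days 140 to 168 of 112 to 168). In the SAP example the carried value, 7.0 against a baseline of 7.95, is a non-response. The contrast with the VOC rule is therefore real only for some participants.

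A reader might also infer that the issue is worse for 900 mg. No 900 mg figure supports this. With equal labels the excess relative to all-fail is x(1 − m)/(1 − x), for example 1.5/27.0 = 5.6%, whatever the size of the effect.

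**Conclusion.** The point holds as a gap in robustness, not as a demonstrated bias. The primary responder status of transfused participants depends on a recorded reason that is undefined, is not adjudicated and may be influenced by Hb, and neither planned check tests that dependence. Under the assumed rates (5% to 15% transfused, carried-forward response 40% against 10%), the plan's difference is about 1 to 4 points larger than with every transfusion scored as non-response. It is not generally larger than with carry-forward for all. This mechanism creates no effect where voxelotor has none on Hb, and the >95% power for 1500 mg is safe under either rule. What may shift is the reported size of the effect. The transfusion rates, label shares and Hb distributions are all assumptions, because the documents give none.

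**What to change.** Keep the pre-specified primary rule. Data from 156 of the 274 participants have already been unblinded, including to sponsor biostatistics staff (SAP Sections 2 and 6.2), so rewriting the primary derivation now would be a debatable change of estimand.

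Before Group 2b is unblinded, add to SAP 6.3.5.1 and 8.2.1 a required sensitivity analysis that scores any RBC transfusion in the window as non-response whatever the recorded reason. Apply it to the primary test and to hypothesis 5 (900 mg against placebo), and report it with counts of transfused participants by arm and reason. It does not use the label, so it needs no adjudication. It concerns endpoint classification only.

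The cost is a short extra derivation and two further comparisons, with no new data. Response rates in that analysis may be a few points lower than in the primary one.
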